8.11.3.9 In-hospital MACCE

The total number and percentage of in-hospital MACCE. MACCE is defined as one or more of the following events: All cause death, Acute Myocardial Infarction (AMI), Coronary Artery Bypass Grafting (CABG), Repeat Coronary Revascularization of the target lesion, Acute Ischemic Stroke (AIS) during hospitalization for the PCI procedure.

Document ID:	<As applicable, per local requirements>	Document title:		Classification:	For internal use
		Statistical Analysis Plan			
Modified:	11MAY2023			Author:	
Version:	3.0	Template ID:	ClinicalStudyTemplate0025	Approver:	
Status:	Final	Template Version Date:	02MAR2018	Page:	36 of 52

Statistical Analysis Plan

Descriptive summaries of MACCE will be presented by treatment group for the FAP and the PP population and will include the number of subjects with non-missing data (n), percentages and 95% exact confidence intervals.

The between treatment group difference in MACCE will be tested using a Chi-square test. If a Chi square analysis is not possible (i.e. >20% of the expected cell frequencies less than 5), then a Fisher's exact test will be performed instead. The two-sided p-value of this test will be presented. When the p-value is lower than the significance level of 5% (alpha) we will reject the null hypothesis of equal in-hospital MACCE in both treatment groups.

All subjects in the FAP population will be included in this analysis. The analysis will be repeated for the PP population.

8.12 Safety Analysis

All safety analysis will be performed on the Safety Population. The percentages will be calculated using the number of subjects in the Safety Population as the denominator.

8.12.1 In-hospital MACCE

The number and percentage of subjects with MACCE will be summarized for the Safety population. Also number and percentage of subjects in each of the subcategories of MACCE will be presented, i.e. All cause death, Acute Myocardial Infarction (AMI), Coronary Artery Bypass Grafting (CABG), Repeat Coronary Revascularization of the target lesion, Acute Ischemic Stroke (AIS) during hospitalization for the PCI procedure. In addition, the number of reported cases of MACCE will be summarised.

All deaths and in-hospital MACCE will be listed.

8.12.2 Duration until discharge

Duration until discharge will be calculated and summarized by actual treatment group for the Safety population.

8.12.3 Device deficiencies

Device deficiencies will be listed and summarized for the DCR group for the Safety population.

Document ID:	<As applicable, per local requirements>	Document title:		Classification:	For internal use
		Statistical Analysis Plan			
Modified:	11MAY2023			Author:	
Version:	3.0	Template ID:	ClinicalStudyTemplate0025	Approver:	
Status:	Final	Template Version Date:	02MAR2018	Page:	37 of 52

Statistical Analysis Plan

8.12.4 Laboratory measurements

Hemoglobin value (g/dl), serum creatinine (SCr) baseline measurements (mg/dl) and highest post-PCI serum creatinine (SCr) measurement (mg/dl) will be summarized by treatment group for the Safety Population. Estimated eGFR (ml/min/1.73m²) at baseline and post PCI will be summarized as continuous variables and in categories (Stage I normal renal function/Stage II mild – moderate reduction/ Stage III moderate – severe reduction/ Stage IV severe reduction/ Stage V renal failure).

8.13 Subgroup Analysis

As exploratory analyses the primary endpoint will be analyzed by 1, 2, 3 or more vessel PCI and by anatomical complexity as derived from SYNTAX score in tertiles (see Section 6).

We will also analyze the primary and secondary endpoint in the DCR arm of the PP population by overall quality and accuracy of the roadmap divided into 3 groups: very good or good, fair and poor or very poor, also comparing 1 vessel PCI vs. multi vessel (2 or more vessel) PCI. We will also assess the overall quality and accuracy of the roadmap for 1 vessel PCI vs multi vessel (2 or more vessel) PCI. Here “very good” or “good” is indicated when the roadmap shows the coronary artery tree correctly (no missing relevant arteries and no significant artefacts in the roadmap) and the roadmap overlay location is in the correct location during vast majority of the PCI (comparing roadmap location with e.g. interventional guiding catheter, guidewire and device location). The score “fair” is indicated when the roadmap misses some arteries but is still useful (showing the overall artery tree correctly) and/or the roadmap overlay location is not always correct but is correct sufficiently to provide navigation guidance during the PCI. The roadmap is scored “poor” or “very poor” when the roadmap misses relevant arteries and not providing a correct overall artery tree overview and/or the roadmap overlay location is not correct majority of the PCI and not usable for PCI navigation guidance. Scoring the overall quality and accuracy of the roadmap during PCI is left to investigator discretion.

8.14 Adjustment for Covariates

Analyses to determine whether there is an effect based on e.g. intervention difficulty (as measured by the SYNTAX score), lesion characteristics, patient demographics, physician experience, center etc. will be performed. If an effect on the primary or secondary endpoint is found, applying adjustment analysis will be considered. As a sensitivity analysis, we will then perform an analysis

Document ID:	<As applicable, per local requirements>	Document title:		Classification:	For internal use
Modified:	11MAY2023	Statistical Analysis Plan		Author:	
Version:	3.0	Template ID:	ClinicalStudyTemplate0025	Approver:	
Status:	Final	Template Version Date:	02MAR2018	Page:	38 of 52

Statistical Analysis Plan

of covariance (ANCOVA) for the primary and/or the secondary endpoint adjusting for covariates which are deemed important. The results of the ANCOVA will be displayed through Least-Squares Means (LSMEANS) estimates of the between treatment group difference (with 95% confidence intervals) and the p-value for the between treatment group difference adjusted for covariates.

To investigate whether there is a center effect on the primary outcome, we will calculate the Intra Class Correlation coefficient (ICC) of the total iodinated contrast volume between centers. The ICC is the ratio of the variability between centers to the total variance. The ICC measures to what extent the proportion of the total variability of the primary outcome is accounted for by the clustering of patients within centers. If the ICC is higher than 0.10 we will perform a random effects model on the primary outcome with center as a random effect and treatment as a fixed effect. We will also check the distribution of baseline characteristics between centers. If the centers differ in characteristics, which may influence the primary outcome, such as intervention difficulty, lesion characteristics, patient demographics, physician experience etc, we will perform a random effects model on the primary outcome with center as a random effect and treatment and other covariates as fixed effects (ANCOVA) as a sensitivity analysis. The results of the ANCOVA will be displayed through Least-Squares Means (LSMEANS) estimates of the between treatment group difference (with 95% confidence intervals) and the p-value for the between treatment group difference adjusted for covariates.

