7.3. Poolability

A site effect analysis will be conducted on the primary endpoint to assess poolability of data. Adjustment analysis will be considered if sites are not homogeneous.

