8.1.1 Sample Size Justification Primary Endpoint

A recent single center, non-randomized, retrospective study [Yabe 2018] has shown to achieve 21.9% contrast reduction when using Dynamic Coronary Roadmap compared to the control group without using Dynamic Coronary Roadmap, see Table 2.

	Control group	DCR group
Number of patients	103	43
Iodinated contrast volume (ml) average \pm standard deviation	152.1 ± 73.0	118.8 ± 49.7

Table 2 Results of a recent pilot study [Yabe 2018]

To determine the sample size for the primary endpoint of this study we used the Yabe study outcomes as input with a margin of 7% for the contrast reduction, i.e., the sample size calculation is performed to reliably show a 15% contrast reduction in the DCR group compared to the control group not using Dynamic Coronary Roadmap.

For the sample size and power calculations we have set:

- Estimated mean for the Control group = 152.1 (based on [Yabe 2018])
- Estimated mean for the DCR group = 129.3 (15% reduction)
- Estimated standard deviation = 73.0 (based on [Yabe 2018])
- Effect size (standardized difference): $(152.1 - 129.3)/73.0 = 0.3123$
- Significance: one-sided $\alpha = 0.025$ (the type I error, i.e., probability of rejecting a true null hypothesis)

Document ID:	<As applicable, per local requirements>	Document title:		Classification:	For internal use
		Statistical Analysis Plan			
Modified:	11MAY2023			Author:	
Version:	3.0	Template ID:	ClinicalStudyTemplate0025	Approver:	
Status:	Final	Template Version Date:	02MAR2018	Page:	21 of 52

Statistical Analysis Plan

- Power (1- β) = 80%

Sample sizes of 162 for each group achieves 80% power to reject the null hypothesis of equal means when the population mean difference is 15% with a standard deviation of 73.0 for both groups and with a significance level (alpha) of 0.025 using a one-sided two-sample equal-variance t-test (calculated by PASS 16.0.3 software).

Finally the percentage of subjects that are expected to be lost at random during the course of the study (drop-out rate) and for whom no response data will be collected (i.e., will be treated as "missing") needs to be taken into account. A drop-out rate of 10% (DR=0.1) is assumed, meaning that $162/(1-DR)=180$ patients are needed in each group totaling 360 patients for the primary endpoint.

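### The site analysis promised to assess poolability examines differences in site means only; nothing in the SAP assesses whether the device effect differs between sites

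*SAP*

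**What the plan says.** Protocol 7.3 commits to the check and states its purpose: "A site effect analysis will be conducted on the primary endpoint to assess poolability of data". It names no method, and says only that adjustment will be considered if sites turn out not to be homogeneous. The protocol's revision history lists the analysis among the additions made after regulatory pre-submission feedback.

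SAP 8.14 is the only place that supplies a method. It calculates an ICC of total contrast volume between centers, defined thus: "The ICC is the ratio of the variability between centers to the total variance". The consequence is "If the ICC is higher than 0.10 we will perform a random effects model on the primary outcome with center as a random effect". That model gives the device a single fixed effect, common to all centers. A second route in 8.14 compares baseline characteristics between centers and, if they differ, adds covariates to the same kind of model as a sensitivity analysis.

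SAP 8.2 adds that the main data will be shown by clinical site. The table list in SAP section 11 has by-site tables for enrolment and randomization, but none for efficacy. Neither document mentions a treatment-by-site interaction, a random treatment slope, site-specific treatment differences with confidence intervals, or what to do if the effect differs between sites.

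**The concern.** Pooling a treatment comparison is a question about the treatment effect: is it similar enough across sites for one average to describe it? The ICC answers another question, namely how far sites differ in overall contrast use. Because allocation is 1:1 and stratified by site (SAP 4.4.2), site differences shared by both arms largely cancel from the comparison. A difference in the device effect reaches the site means only at half strength, since only half of each site's subjects receive the device. So the ICC can be high when the effect is uniform and low when it is not.

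This matters here because the trial is unblinded, operators control how much contrast they inject, and SAP 4.5 itself names site differences and user preferences as sources of bias. Protocol 4.3 chose a multi-center design so that the result would generalize. As planned, the report could say that a site analysis was done for poolability although the effect had never been compared across sites.

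**Working it through.** **Inputs.** From SAP 8.1.1: "Estimated mean for the Control group = 152.1"; device-group mean 129.3 ml, so a planned effect of 152.1 − 129.3 = 22.8 ml; "Estimated standard deviation = 73.0"; one-sided alpha 0.025; dropout 10%. From SAP 8.1: 394 subjects and at least 5 centers. Assumed, because the documents give no figure: 6 to 10 equal sites, normal data, the same SD in every site and arm, and a background ICC between 0 and 0.10. Evaluable subjects: 394 × 0.9 = 354.6, taken as 354.

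**The plan's own figure.** "Sample sizes of 162 for each group achieves 80% power". The normal approximation gives 161 per group for 22.8 ml and SD 73. The noncentral t gives 162, with power 80.03%, and 162/0.9 = 180. The stated figures reproduce.

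**What the ICC can see.** Let the saving be d1 at half the sites and d2 at the rest, with equal control means.
- Gap between the two groups of site means = (d1 − d2)/2.
- Between-site variance = ((d1 − d2)/4)².
- Treatment-adjusted ICC = between-site variance / (between-site variance + 73²), with 73² = 5329.

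| Saving at half / other half (ml) | Between-site variance | ICC |
|---|---|---|
| 22.8 / 0 | 5.7² = 32.49 | 0.006 |
| 33.3 / 0 (pilot difference, 152.1 − 118.8) | 8.325² = 69.31 | 0.013 |
| 45.6 / 0 (average 22.8, as planned) | 11.4² = 129.96 | 0.024 |
| 22.8 / −22.8 (opposite effects) | 11.4² = 129.96 | 0.024 |

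Leaving the ICC unadjusted for treatment changes these by 0.001 or less. To reach 0.10 from effect differences alone, (d1/4)² must equal 5329 × 0.10/0.90 = 592.1, so d1 = 4 × 24.33 = 97.3 ml at half the sites and 0 at the rest. That is 97.3/152.1 = 64% of the control mean. The unadjusted ICC requires 110.4 ml, or 73%.

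**How often the rule fires.** Simulated trials used the ANOVA estimator of the ICC, about 354 evaluable subjects and 6 to 10 sites. The 0.02 row comes from runs sized on 394 without dropout.

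| Background ICC from other site differences | 45.6 ml at half the sites, 0 at the rest | 22.8 ml at every site |
|---|---|---|
| 0 | under 0.5% | about 0% |
| 0.02 | 4–6% | 0.2% |
| 0.05 | about 20–24% | about 6–10% |
| 0.10 | about 50% | about 40% |

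The trigger mainly follows the background ICC (down each column) and responds much less to the pattern of effect (across each row). When it does fire, the model fitted still has one common effect.

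**What a direct assessment can see.** A treatment-by-site F test at the 0.15 level (an assumed level) flags about 70–78% of trials with 45.6 versus 0 ml, and 14–15% when the effect is uniform, as it should. For 22.8 versus 0 ml it flags only about 29–36%.

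**The case against.** Four points against the concern have force.

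- SAP 8.14 never uses the word poolability, and no passage says that an ICC at or below 0.10 means the data may be pooled. A reader might infer that the SAP would declare a half-site effect poolable. The documents do not support that; they leave poolability of the effect undefined.
- A reader might also infer that a half-site effect would nearly always escape the rule. That holds only when usual contrast use is similar across sites. With background variation the rule fires more often, as the table shows, though for reasons mostly unrelated to the device.
- The ICC rule has a proper use. The primary t-test ignores site, and modelling center when between-site variance is large can improve the precision of the estimate. There is no case for dropping the rule.
- An interaction test is itself weak for modest differences, so a p-value threshold cannot define poolability either.

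SAP 8.2 is partial mitigation: by-site summaries would let a reader compare arms within a site informally. It specifies no site-specific difference, interval or rule. The baseline comparison in 8.14 leads only to another common-effect model. The core of the point therefore stands.

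**Conclusion.** The concern holds in this form: the site analysis that Protocol 7.3 promises for poolability is implemented in SAP 8.14 as a check on site means, and a device effect that differs between sites would go unassessed. A pattern as marked as double the planned effect at half the sites and none at the others adds only about 0.024 to an ICC judged against 0.10.

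The gap concerns the statement on poolability and generalizability. A reader might infer that the primary result is compromised. It is not: the primary hypothesis concerns the average effect, and nothing here biases that estimate or inflates its type I error. The percentages rest on equal sites, normal data and a common SD of 73 ml. The SAP does not say whether the ICC is adjusted for treatment or taken on the log scale. On the raw scale, adjusted and unadjusted versions lead to the same conclusion; the log scale was not examined.

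**What to change.** In SAP 8.14, keep the ICC and the center model as the check on site means, and state whether the ICC is adjusted for treatment and on which scale it is calculated. Add a supportive poolability assessment on the scale of the primary analysis:

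1. Site-specific treatment differences with 95% CIs in a forest plot, with very small sites combined by a stated rule.
2. A model with treatment, site and treatment-by-site (or a random treatment slope), reporting the between-site variation in effect and an interaction p-value at a pre-stated level, for example 0.15. If flagged, show the random-slope estimate beside the primary result.
3. A sentence saying that a non-significant interaction does not prove poolability, because power is low for small differences (about 29–36% at the 0.15 level for 22.8 versus 0 ml). The estimates and intervals should carry the interpretation.

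The cost is SAP wording, one model and one figure from data already collected. The primary test and the sample size do not change.

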8.15 Multiple Comparison and Multiplicity

No adjustments for multiplicity will be made. The primary and secondary endpoint will be tested with a one-sided alpha of 2.5%.

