8.1.2 Sample Size Justification Secondary Endpoint

A recent single center, non-randomized, prospective study [Rajappan 2017] showed a 25.6% reduction in the median number of cine X-ray runs after introduction of Dynamic Coronary Roadmap, see Table 3.

	Enrollment group 1	Enrollment group 4
Number of patients	21	21
Number of cine X-ray runs	Average: 46.2 SD: 22.4 Median: 43.0 IQR: 31-54	Average: 34.6 SD: 21.2 Median: 32.0 IQR: 20-43
Number of stents	Average: 1.76 SD: 0.89	Average: 1.67 SD: 0.86

Table 3 Results of a recent pilot study [Rajappan 2017]

For the sample size and power calculations we have set based on [Rajappan 2017]:

- Estimated mean for the Control group = 46.2
- Estimated mean for the DCR group = 34.6

Document ID:	<As applicable, per local requirements>	Document title:	Classification:	For internal use
Modified:	11MAY2023	Statistical Analysis Plan		
Version:	3.0	Template ID:	ClinicalStudyTemplate0025	Approver:
Status:	Final	Template Version Date:	02MAR2018	Page: 22 of 52

Statistical Analysis Plan

- Estimated median for the Control group = 43.0
- Estimated median for the DCR group = 32.0
- Significance: one-sided $\alpha = 0.025$ (the type I error, i.e., probability of rejecting a true null hypothesis)
- Power $(1-\beta) = 80\%$

Sample sizes of 177 for each group achieves 80% power to reject the null hypothesis of equal population distributions with a significance level (alpha) of 0.025 using a one-sided Wilcoxon-Mann-Whitney test, since the number of angiographic X-ray runs is discrete and is likely to be not normally distributed (calculated by SAS software).

This means for the secondary endpoint on Number of Angiograms that $177/(1-DR)=197$ patients are needed in each group, so 394 in total which is higher than the total number of patients (360) required for the primary endpoint, so **a total of 394 subjects are required for this study.**

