8.2 General Considerations

All results will be summarized by treatment group using the following descriptive statistics: n, mean with 95% confidence intervals, standard deviation (SD), median, interquartile range (IQR), minimum and maximum. Categorical data will be summarised for each treatment group as the number and percentage of subjects in each category (including the category 'missing' if applicable). Generally, percentages will be calculated for missing categories and all percentages will be based on total number of subjects in the population (denoted by N on the summary tables and figures) Statistical analysis will be performed using SAS (SAS® Life Science Analytics Framework 5.1.2) and/or R statistical software (<https://www.r-project.org/>).

All data will be listed for the enrolled population. The data will be sorted by treatment group, subject number and date of assessment (if applicable).

All hypotheses will be tested at a 2.5% level of significance using a one-sided test unless otherwise specified.

For summary statistics, the mean and median will be displayed to one decimal place greater than the original value and the measure of variability (e.g., SD) will be displayed to two decimal places greater than the original value. Minimum and maximum will be reported to the same decimal places as the original value. Percentages will be displayed to 1 decimal place. P-values will be reported to three decimal places; p-values less than 0.001 will be reported as $p<0.001$.

Summary tables will have treatment columns labelled as 'Dynamic Coronary Roadmap' or 'Control'. The main data will also be presented per clinical site.

Document ID:	<As applicable, per local requirements>	Document title:		Classification:	For internal use
		Statistical Analysis Plan			
Modified:	11MAY2023			Author:	
Version:	3.0	Template ID:	ClinicalStudyTemplate0025	Approver:	
Status:	Final	Template Version Date:	02MAR2018	Page:	23 of 52

Statistical Analysis Plan

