8.11.3 Exploratory Efficacy Analysis

8.11.3.1 Contrast Volume per Vessel PCI

The average undiluted iodinated contrast volume (in ml) used per vessel PCI (from first positioning the interventional guiding catheter in stable coronary position till end of PCI procedure) by treatment group. For multi vessel PCI the iodinated contrast volume used per vessel PCI will be determined based on the total PCI contrast volume (from first positioning the interventional guiding catheter in stable coronary position till end of PCI procedure) divided by the number of vessels actually treated by PCI.

Descriptive summaries of the total undiluted iodinated contrast volume divided by the actual number of vessels treated by PCI will be presented by treatment group for the FAP and the PP population and will include the number of subjects with non-missing data (n), mean with 95% confidence interval, standard deviation (SD), median, interquartile range (IQR) and minimum and maximum values.

The endpoint will be evaluated using a one-sided two-sample t-test. We will test for assumptions, e.g. normality and equal variances. Normality will be checked using histograms and Q-Q plots. If there are strong indications of non-normality, the data will be (log)transformed, and the back transformed results will be presented. Levene's test for equality of variances will be applied. When the p-value of this test is greater than 0.05, then we assume the variances are equal and we will use the arithmetic mean of the variances in calculating the standard error. When the p-value is less than or equal to 0.05, then we assume

Document ID:	<As applicable, per local requirements>	Document title:		Classification:	For internal use
		Statistical Analysis Plan			
Modified:	11MAY2023	Template ID:	ClinicalStudyTemplate0025	Author:	
Version:	3.0	Template Version Date:	02MAR2018	Approver:	
Status:	Final			Page:	31 of 52

Statistical Analysis Plan

the variances are unequal and then we will calculate the standard error from the weighted average of the two variances.

The results of the t-test will be displayed as estimates of the between treatment group difference (with 95% confidence intervals) and the (one-sided) p-value for the between treatment group difference. When the p-value is lower than the significance level of 2.5% (alpha) we will reject the null hypothesis.

All subjects in the FAP population will be included in this analysis. The analysis will be repeated for the PP population.

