8.11.3.2 Contrast Volume per Stratification Group (1, 2, 3 or more vessel PCI)

The total undiluted iodinated contrast volume (in ml) used per PCI (from first positioning the interventional guiding catheter in stable coronary position till end of PCI procedure) in each stratification group, i.e., 1 vessel PCI, 2 vessel PCI and 3 or more vessel PCI.

Descriptive summaries of the total undiluted iodinated contrast volume will be presented by treatment group and by stratification group (1 vessel PCI, 2 vessel PCI and 3 or more vessel PCI) for the FAP and the PP population and will include the number of subjects with non-missing data (n), mean with 95% confidence interval, standard deviation (SD), median, interquartile range (IQR) and minimum and maximum values.

The endpoint will be evaluated per subgroup (1 vessel PCI, 2 vessel PCI and 3 or more vessel PCI) using a one-sided two-sample t-test. We will test for assumptions, e.g. normality and equal variances. Normality will be checked using histograms and Q-Q plots. If there are strong indications of non-normality, the data will be (log)transformed, and the back transformed results will be presented. Levene's test for equality of variances will be applied. When the p-value of this test is greater than 0.05, then we assume the variances are equal and we will use the arithmetic mean of the variances in calculating the standard error. When the p-value is less than or equal to 0.05, then we assume the variances are unequal and then we will calculate the standard error from the weighted average of the two variances.

The results of the t-test will be displayed as estimates of the between treatment group difference (with 95% confidence intervals) and the (one-sided) p-value for the between treatment group difference. When the p-value is lower than the significance level of 2.5% (alpha) we will reject the null hypothesis.

All subjects in the FAP population will be included in this analysis. The analysis will be repeated for the PP population.

Document ID:	<As applicable, per local requirements>	Document title:		Classification:	For internal use
		Statistical Analysis Plan			
Modified:	11MAY2023			Author:	
Version:	3.0	Template ID:	ClinicalStudyTemplate0025	Approver:	
Status:	Final	Template Version Date:	02MAR2018	Page:	32 of 52

Statistical Analysis Plan

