8.11.3.3 Contrast Volume per Simple, Intermediate, Complex PCI subgroup

The total undiluted iodinated contrast volume (in ml) used per PCI (from first positioning the interventional guiding catheter in stable coronary position till end of PCI procedure) in subgroups of simple, intermediate and complex PCI.

Descriptive summaries of the total undiluted iodinated contrast volume will be presented by treatment group and by complexity in tertiles for the FAP and the PP population and will include the number of subjects with non-missing data (n), mean with 95% confidence interval, standard deviation (SD), median, interquartile range (IQR) and minimum and maximum values.

The endpoint will be evaluated per subgroup using a one-sided two-sample t-test. We will test for assumptions, e.g. normality and equal variances. Normality will be checked using histograms and Q-Q plots. If there are strong indications of non-normality, the data will be (log)transformed, and the back transformed results will be presented. Levene's test for equality of variances will be applied. When the p-value of this test is greater than 0.05, then we assume the variances are equal and we will use the arithmetic mean of the variances in calculating the standard error. When the p-value is less than or equal to 0.05, then we assume the variances are unequal and then we will calculate the standard error from the weighted average of the two variances.

The results of the t-test will be displayed as estimates of the between treatment group difference (with 95% confidence intervals) and the (one-sided) p-value for the between treatment group difference. When the p-value is lower than the significance level of 2.5% (alpha) we will reject the null hypothesis.

All subjects in the FAP population will be included in this analysis. The analysis will be repeated for the PP population.

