8.11.3.4 Acute Kidney Injury (AKI) Incidence

The total number and percentage of subjects in which Acute Kidney Injury (AKI) diagnosed after PCI. AKI is defined as an absolute SCr increase >0.3 mg/dl within 48 hours post PCI or a relative SCr increase $>50\%$ within 7 days post PCI, or eGFR decrease $>25\%$ within 48 hours post PCI.

Descriptive summaries of AKI incidence will be presented by treatment group for the FAP and the PP population and will include the number of subjects with non-missing data (n), percentages and 95% exact confidence intervals.

Document ID:	<As applicable, per local requirements>	Document title:		Classification:	For internal use
		Statistical Analysis Plan			
Modified:	11MAY2023			Author:	
Version:	3.0	Template ID:	ClinicalStudyTemplate0025	Approver:	
Status:	Final	Template Version Date:	02MAR2018	Page:	33 of 52

Statistical Analysis Plan

The between treatment group difference in AKI incidence will be tested using a Chi-square test. If a Chi square analysis is not possible (i.e. >20% of the expected cell frequencies less than 5), then a Fisher's exact test will be performed instead. The two-sided p-value of this test will be presented. When the p-value is lower than the significance level of 5% (alpha) we will reject the null hypothesis of equal procedural success in both treatment groups.

All subjects in the FAP population will be included in this analysis. The analysis will be repeated for the PP population.

When considering the incidence of AKI in the patient population of this trial (7.1% incidence, but reported from 3% to 19% [Tsai 2014a]) and taking into account the sample size of 394 patients it is not likely this trial will find a significant difference in AKI incidence in the DCR group compared to the control group.

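### The powered secondary endpoint is tested at the full one-sided 2.5% with no condition on the primary; a fixed sequence would close the gap without changing the sample size.

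*SAP*

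**What the plan says.** SAP 8.15 is the whole multiplicity plan: "No adjustments for multiplicity will be made. The primary and secondary endpoint will be tested with a one-sided alpha of 2.5" per cent. SAP 8.2 sets the same level for each test: "All hypotheses will be tested at a 2.5% level of significance using a one-sided test unless otherwise specified".

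SAP 8.11.2 (and protocol 7.7.1) state a null and an alternative hypothesis for the number of angiograms and choose a one-sided Wilcoxon-Mann-Whitney test. SAP 8.11.2 adds a rejection rule at 2.5% in the FAP, repeated in the per-protocol population. The rule carries no condition on the primary.

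SAP 8.1.2 (protocol 7.1.1) powers this endpoint at 80% and lets it set the trial size. Its 394 subjects is a number "which is higher than the total number of patients (360) required for the primary endpoint".

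The exploratory sections, SAP 8.11.3.1 to 8.11.3.9, also carry formal rejection rules. One example, from 8.11.3.2, is "When the p-value is lower than the significance level of 2.5% (alpha) we will reject the null hypothesis".

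**The concern.** An endpoint with its own hypotheses, alpha, power statement and influence on the sample size is one from which the sponsor evidently means to draw a conclusion. The plan tests it in parallel with the primary, at the same level and in no stated order. If contrast volume misses significance and the angiogram count reaches it, the SAP's rule formally rejects the secondary null and says nothing about what that rejection is worth. The 2.5% attached to each test does not bound the chance of a false rejection across the pair.

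What is at stake is the reading of the secondary result, not the validity of the primary test.

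**Working it through.** **Inputs.** From SAP 8.1.1: means 152.1 and 129.3 ml, SD 73.0, one-sided alpha 0.025, 80% power, 162 per group, 10% drop-out. From SAP 8.1.2: 177 evaluable per group and 80% power for the secondary. From SAP 8.15: one-sided 2.5% for each endpoint. The correlation ρ between the two test statistics is not given, so I take 0 to 0.9 as an assumption.

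**1. The plan's own figures.** Standardised difference = (152.1 − 129.3)/73.0 = 0.3123. A one-sided equal-variance t-test (noncentral t) with 162 per group has power 80.03%, so 162 is reproduced. Drop-out: 162/0.9 = 180 per group (360 in total); 177/0.9 = 196.7, rounded up to 197 per group (394 in total). With 177 evaluable per group the primary has 83.4% power. The 177 itself depends on a distribution that the documents do not state. I take it as given, and nothing below turns on how it was derived.

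**2. False rejections, both nulls true.** Treat the two statistics as bivariate standard normal with critical value 1.96, and let B(ρ) be the probability that both exceed it.

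- P(at least one rejection) = 0.025 + 0.025 − B(ρ)
- P(secondary rejects, primary does not) = 0.025 − B(ρ)

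| ρ | B(ρ) | At least one | Secondary only |
|---|---|---|---|
| 0 | 0.0006 | 4.9% | 2.4% |
| 0.5 | 0.0046 | 4.5% | 2.0% |
| 0.7 | 0.0083 | 4.2% | 1.7% |
| 0.9 | 0.0148 | 3.5% | 1.0% |

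The excess over 2.5% arises only when both nulls are true. If only one null is true, the only possible false rejection is in that endpoint, at 2.5%.

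**3. Under a fixed sequence.** If the primary null is true, no false rejection can occur unless the primary rejects, which has probability 2.5%. If the primary null is false, the only possible false rejection is in the secondary, at no more than 2.5%. The pair is held at 2.5% for any ρ. The primary is still tested at 2.5%, so its 83.4% power and the 394 subjects are unchanged.

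**4. What the sequence gives up.** With primary power 83.4% and secondary power 80%, P(secondary significant, primary not) = 0.80 − P(both significant). At ρ = 0 this is 0.80 × (1 − 0.834) = 13.3%. It is 9.0% at 0.5, 6.6% at 0.7 and 3.2% at 0.9. The 16.6% chance that the primary misses (1 − 0.834) is not the cost, because some of those trials would miss on the secondary too.

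**5. The alternative of splitting alpha.** At one-sided 1.25% each, the primary would need 197 evaluable per group, that is 219 per group or 438 in total after drop-out. With 177 evaluable its power would be 75.4%.

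**6. Exploratory rules in the FAP.** One-sided at 2.5%: per vessel 1, vessel groups 3, SYNTAX tertiles 3, fluoroscopy and procedure time 2, dose-area product and air kerma 2, making 11. At 5%: acute kidney injury, variability, procedural success and in-hospital events, making 4. If all 15 were independent, P(any rejection under the nulls) = 1 − 0.975^11 × 0.95^4 = 38.3%. Independence is not credible, since seven of the 15 reuse contrast volume.

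**The case against.** The plan exceeds no error rate that it states. SAP 8.2 and 8.15 give 2.5% per test, neither document promises a familywise rate, and 8.15 declares openly that no adjustment is made. There is one primary endpoint with one FAP test, and its error stays at 2.5%. All of this stands. The choice is disclosed and contradicts nothing; what is missing is a rule for reading the secondary.

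A reader might infer that the plan lets an efficacy claim rest on the secondary alone, or that the trial's error rate is nearly doubled. The documents do not support either reading. No sentence says that trial success may rest on the secondary, and the only hypothesis listed with the objectives concerns contrast volume (protocol 5.1, SAP 3.1). The near doubling belongs to zero correlation. The two endpoints are mechanically linked, since protocol 6.4.1.2 puts a typical run at 7 ml of contrast, so the lower part of the range is plausible.

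A reader might also take the 38% as the chance of a spurious efficacy finding. It is an upper illustration under independence, and the four tests at 5% can reject in either direction. These analyses are called exploratory throughout. Both documents call a significant difference in kidney injury unlikely, and the protocol says the same of procedural success and in-hospital events. The label deals with most of this, and what remains is wording.

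**Conclusion.** The point holds as a gap in SAP 8.15 and 8.11.2. A powered secondary endpoint that sets the sample size is tested at the full one-sided 2.5%, with no condition on the primary and no statement of how to read it if the primary misses. With both nulls true, the chance of at least one false rejection across the pair is 3.5% to 4.9%. This rests on a bivariate normal approximation and an assumed correlation of 0.9 to 0. The primary conclusion is not affected. That the secondary is tested whatever the primary shows is inferred from the absence of any gate; no sentence says so. The change is a cheap improvement worth making, not the repair of an invalid analysis.

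**What to change.** In SAP 8.15, replace the present statement with a fixed sequence. The secondary endpoint is tested formally, at one-sided 2.5% in the FAP, only if the primary is significant at one-sided 2.5% in the FAP. Otherwise it is reported descriptively with a nominal p-value. Refer to this rule from 8.11.2.

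The cost is SAP text and the 3% to 13% chance, under the planning assumptions, of a positive secondary that cannot be formally claimed. No subjects are added and no primary power is lost. The SAP is already at Final 3.0, and its table list names a log-transformed primary analysis, so the change should be recorded in section 9.2 with its date and justification.

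A minor wording point: in 8.11.3.1 to 8.11.3.9, drop the rejection rules, label the p-values nominal, and keep the estimates and intervals. This would also remove a slip in 8.11.3.4, where the kidney-injury rule ends "we will reject the null hypothesis of equal procedural success in both treatment groups".
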